2.0 Abbreviations

CDAI	Crohn's Disease Activity Index
CRF	Case Report Form
CRP	C-Reactive Protein
DLQI	Dermatology Life Quality Index
EU	European Union
FPFV	First Patient First Visit
FPLV	First Patient Last Visit
GCP	Good Clinical Practice
HAQ-DI	Health Assessment Questionnaire–Disability Index
ICH	International Conference on Harmonization
IEC	Independent Ethics Committee
IMID	Immune-Mediated Inflammatory Diseases
IRB	Independent Review Board
K10	Kessler Psychological Distress Scale
LPFV	Last Patient First Visit
LPLV	Last Patient Last Visit
PASI	Psoriasis Area and Severity Index
PDF	Portable Document Format
PP	Per Protocol
PPD	Purified Protein Derivative
PRO	Patient-Reported Outcomes
QoL	Quality of Life
RA	Rheumatoid Arthritis
RAP	Reporting and Analysis Plan
SAE	Serious Adverse Event
SAP	Statistical Analysis Plan
SD	Standard Deviation
SIBDQ	Short Inflammatory Bowel Disease Questionnaire
SOP	Standard Operating Procedure
TNF	Tumour Necrosis Factor
WHODAS 2.0	The World Health Organisation Disability Assessment Schedule 2.0
WPAI:GH	The Work Productivity and Activity Impairment Questionnaire: General Health V2.0

4.0 Abstract

Title: An Observational Study of the Effectiveness of Adalimumab on Health and Disability Outcomes in New Zealand Patients with Immune-Mediated Inflammatory Diseases (VITALITY)

Rationale and Background: For public health purposes disability is becoming increasingly important as an outcome measure. Despite this, there are few data on the effectiveness of adalimumab on disability outcomes in patients with Immune-Mediated Inflammatory Diseases (IMIDs), particularly in the Phase IV setting. There are even less data available in New Zealand, which did not have the opportunity to participate to a major extent in large, multinational, Phase III pivotal studies of adalimumab in IMIDs.

The World Health Organisation Disability Assessment Schedule (WHODAS) 2.0 is a simple, validated, free and easy-to-use generic assessment instrument for health and disability. It is applicable across cultures, in all adult populations. It is a responsive measure that can show what difference a treatment makes.

Results from study of effect of adalimumab on WHODAS scores and other Patient-Reported Outcomes (PRO) of work activity and well-being will be of interest to a variety of stakeholders in the healthcare system including patients, healthcare practitioners and payers.

Research Question and Objectives: The objective of this study is to assess the effect of adalimumab on health and disability outcomes in patients with the immune-mediated inflammatory diseases of rheumatoid arthritis, Crohn's disease and psoriasis.

Study Design: This is a Phase IV, parallel-group, observational, multicentre study designed to investigate the effectiveness of adalimumab on health and disability outcomes in New Zealand patients diagnosed with, rheumatoid arthritis, Crohn's disease and psoriasis.

Overall, a minimum of approximately 190 subjects with IMIDs are planned to be enrolled in the study at up to 15 sites. Approximately 80 subjects will be enrolled into each of 2 parallel study groups of patients diagnosed with rheumatoid arthritis or Crohn's disease. A minimum of 30 subjects with psoriasis will also be enrolled. All subjects will receive at least 3 months of treatment with adalimumab. Continuation of adalimumab will depend upon the patient meeting "Special Authority" response criteria between 3 and 6 months, which will allow continuing reimbursement of drug supply.

To assess health and disability outcomes, the WHODAS 2.0 score will be assessed at baseline, 2, 4 and 6 months after treatment initiation with adalimumab. In addition, other PROs of work activity and well-being, including the Work Productivity and Activity Impairment Questionnaire: General Health (WPAI:GH) V2.0, Kessler

Psychological Distress Scale (K10), Flourishing Scale, Subject Vitality Scale will also be administered at these time points. Disease-specific PROs that are commonly used in clinical practice (Health Assessment Questionnaire–Disability Index [HAQ-DI], Short Inflammatory Bowel Disease Questionnaire [SIBDQ], Dermatology Life Quality Index [DLQI]), will also be assessed. Variations of these disease-specific indices were used in some of the pivotal Phase III studies for adalimumab.

Population: Subjects will be males and/or females who are attending a routine clinical visit and meet all of the inclusion criteria and none of the exclusion criteria.

Inclusion Criteria:

1. Male and female
2. 18 to 75 years of age, inclusive.
3. Patients with a diagnosis of rheumatoid arthritis, Crohn’s disease or psoriasis who have made a decision with their physician to commence treatment with adalimumab in accordance with routine medical practice and with the approved adalimumab New Zealand datasheet.
4. Patients who have been evaluated for tuberculosis risk factors/exposure for active/latent tuberculosis infection (per local requirements and according to the approved adalimumab New Zealand Datasheet).
5. Subject has voluntarily signed and dated an informed consent form prior to any study-specific procedures.

Exclusion Criteria:

1. Previous treatment with adalimumab
2. Previous treatment with any biologic
3. Severe infection including sepsis, active tuberculosis or opportunistic infection.
4. Moderate to severe heart failure (New York Heart Association Class II/III)
5. Concurrent administration with anakinra
6. Hypersensitivity to adalimumab or its excipients
7. Any condition that in the opinion of the investigator would compromise the subject’s well-being or ability to perform the study requirements.

Variables: The primary outcome variable is change in WHODAS 2.0 response score at 6 months compared to baseline. Secondary outcome variables include WHODAS 2.0 response score at 2 and 4 months compared to baseline and other PRO measures of work activity and well-being, outlined above, at all study time points compared to baseline.

Data Sources: Case Report Forms (CRFs). Collection of data includes but not limited to subject demographics, adverse events, serious adverse events and concomitant medications. The following questionnaires will be utilized to collect data directly from participating subjects:

- WHODAS 2.0
- WPAI:GH V2.0
- K10
- Flourishing Scale
- Subject Vitality Scale
- Disease-specific PROs that are commonly used in clinical practice (HAQ-DI, SIBDQ, DLQI)

Study Size: It is anticipated that the three groups will respond differently to adalimumab treatment over the study period and there is reason to believe that these groups will be different at baseline. Therefore, the sample size will be powered for rheumatoid arthritis and Crohn's disease. Approximately 80 subjects will be enrolled into each of these 2 parallel study groups allowing for detection of within participant effect sizes of approximately 0.40 as statistically significant (2-tailed $\alpha=0.05$) with 90% power. A minimum of 30 subjects with psoriasis will also be enrolled. A minimum number of 190 patients will be enrolled into the study.

Data Analysis: Primary Endpoint Analysis

Change in total WHODAS 2.0 score at 6 months after the initiation of adalimumab, in those patients continuing on adalimumab (responder population), across all indications. This change will be summarised as the mean and 95% confidence interval and will be tested with a paired t-test.

Secondary Endpoint Analyses

- Change in disease-specific indices (HAQ-DI, SIBDQ, DLQI), WPAI:GH, K10, Flourishing Scale, Subject Vitality Scale at 2, 4 and 6 months after the initiation of adalimumab, in those patients continuing on adalimumab (responder population). These changes will be summarised as the means and 95% confidence intervals and will be tested with paired t-tests.
- Change in total WHODAS 2.0 score at 6 months after the initiation of adalimumab, in those patients continuing on adalimumab (responder population), compared with those patients not continuing on adalimumab (non-responders). The mean changes in these two groups will be compared using an independent t-test.

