9.0 Research Methods

9.1 Study Design

This is a Phase IV, parallel-group, observational, multicentre study designed to investigate the effectiveness of adalimumab on health and disability outcomes in New Zealand patients diagnosed with rheumatoid arthritis, Crohn's disease and psoriasis.

The decision to commence treatment with adalimumab is to be made by the patient and the physician before including the patient in this study and has to be clearly separated and independent of the decision to include the patient in the study.

Overall, a minimum of approximately 190 subjects with these three IMIDs are planned to be enrolled in the study at up to 15 sites. Approximately 80 subjects will be enrolled into each of 2 parallel study groups of patients diagnosed with rheumatoid arthritis or Crohn's disease. A minimum of 30 subjects with psoriasis will also be enrolled. All subjects will receive at least 3 months of treatment with adalimumab. AbbVie is not supplying adalimumab; adalimumab is to be used according to the approved adalimumab New Zealand Datasheet and is to be prescribed by the physician under usual and customary practice of physician prescription. Continuation of adalimumab will depend upon the patient meeting the disease-specific response criteria as determined by the investigator

between 3 and 6 months, which will allow continuing reimbursement of drug supply under “Special Authority”.

To assess health and disability outcomes, the WHODAS 2.0 score will be assessed at baseline, 2, 4 and 6 months after treatment initiation with adalimumab. Work productivity will be assessed at these time points using the WPAI:GH V2.0 (8). Psychological distress will be measured using the K10 scale (9). Subject happiness will also be measured, Flourishing Scale (10), Subject Vitality Scale (11). Disease-specific patient reported outcomes (PROs) that are more commonly used in clinical practice; Health Assessment Questionnaire–Disability Index (HAQ-DI) (12), Short Inflammatory Bowel Disease Questionnaire (SIBDQ) (13), Dermatology Life Quality Index (DLQI) (14) will also be assessed. Variations of these disease-specific indices were used in some of the pivotal Phase III studies for adalimumab.

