9.6 Study Size

It is anticipated that the three groups will respond differently to adalimumab treatment over the study period and there is reason to believe that these groups will be different at baseline. Therefore, the sample size will be powered for rheumatoid arthritis and Crohn's disease. Approximately 80 subjects will be enrolled into each of these 2 parallel study groups allowing for detection of within participant effect sizes of approximately 0.40 as statistically significant (2-tailed $\alpha=0.05$) with 90% power. A minimum of 30 subjects with psoriasis will also be enrolled. A minimum number of 190 patients will be enrolled into the study. The maximum number of rheumatoid arthritis and Crohn's disease patients will be N=100 in each arm, respectively.

Psoriasis patients make up a much smaller proportion of the population who currently receive adalimumab therapy in New Zealand. Therefore, a smaller number of patients (N=30) are sought to be enrolled in this study to ensure the trial population is representative of the general patient population. The maximum number of psoriasis patients will be N=50.

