9.8 Data Analysis

9.8.1 Definitions

9.8.1.1 Participant Population

All participants who are recruited into the study and start study medication will be used for analysis. A full analysis set will be used for the analysis of the efficacy outcomes with all available data used for the analyses of each outcome at the relevant time points. Efficacy measures are not assessed after a participant discontinues adalimumab. The exception to this will be the analysis of proportion of patients at 6 months who remain on adalimumab, having satisfied the requirements for application for renewal of subsidy by Special Authority. Any participants for whom this assessment is not available will be assumed to have not met these requirements. The primary population for the evaluation of study safety objectives will be the safety population, defined as all participants enrolled into the trial who started study medication. Safety outcomes will only be considered while the patient is on adalimumab. A standard consort diagram describing participant flow (including loss to follow-up and discontinuations for any reason) through the study will be generated.

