9.8.5 Secondary Efficacy Analyses

The following secondary endpoints will be analysed and summarised using general linear models and paired t-tests. The analyses summarising the changes across all indications will include participant, baseline levels and indication as terms in the analyses. Those analyses analysing changes within indications will use paired t-tests. Mean changes will be summarised with 95% confidence intervals derived from these analyses.

- Change in total WHODAS score 2 and 4 months after the initiation of adalimumab across all indications
- Change in total WHODAS score 6 months after the initiation of adalimumab in each indication
- Changes in WPAI:GI, K10, Flourishing Scale, and Subject Vitality Scale scores at 2, 4 and 6 months after the initiation of adalimumab, across all indications

- Change in disease-specific scores (HAQ-DI, SIBDQ, DLQI) at 2, 4 and 6 months after the initiation of adalimumab, in each indication

The proportion of patients at 6 months who remain on adalimumab, having satisfied the requirements for application for renewal of subsidy by special authority as defined below for each indication will be summarised for all indications combined and separately. These proportions will be summarised with exact 95% confidence intervals.

- **Rheumatoid arthritis:** $\geq 50\%$ decrease in active joint count from baseline AND a clinically significant response to treatment in the opinion of the physician
- **Crohn's disease:** CDAI score reduction by 100 points or CDAI score ≤ 150
- **Psoriasis:** PASI score reduction of $\geq 75\%$; or in the case of a patient had severe chronic plaque psoriasis of the face, or palm of a hand or sole of a foot at the start of treatment, the patient has a reduction in the PASI symptom subscores for all 3 of erythema, thickness and scaling, to slight or better, OR $\geq 75\%$ reduction in affected skin area.

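### The Abstract and Section 9.8 name different populations for the month-2 and month-4 PRO changes, and the Abstract's version, read as eventual continuers, would select on a later outcome

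*Combined protocol and SAP*

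**What the plan says.** The first secondary bullet under Data Analysis in the Abstract (Section 4.0) covers HAQ-DI, SIBDQ, DLQI, WPAI:GH, K10, the Flourishing Scale and the Subject Vitality Scale. It tests change by paired t-test "at 2, 4 and 6 months after the initiation of adalimumab, in those patients continuing on adalimumab (responder population"). The next bullet calls patients who do not continue non-responders.

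Section 9.1 makes continuation depend on disease-specific response criteria being met "between 3 and 6 months, which will allow continuing reimbursement of drug supply". It also states that everyone receives at least three months of treatment. Table 2 schedules the questionnaires at months 2 and 4 for all patients. Sections 9.8.1.1 and 9.9 end efficacy assessment only when adalimumab stops.

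Section 9.8 has no responder restriction. Section 9.8.1.1 takes all who start medication and specifies a full analysis set "with all available data used for the analyses of each outcome at the relevant time points". Section 9.8.2 repeats the full analysis set. Section 9.8.5 lists the generic scales at months 2, 4 and 6 across indications, and "Change in disease-specific scores (HAQ-DI, SIBDQ, DLQI) at 2, 4 and 6 months after the initiation of adalimumab, in each indication". The amendment table in Section 5.0 records no change to either analysis text, so neither supersedes the other.

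**The concern.** The same tests have two populations, and the choice between them could be made after the data are seen.

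The choice matters because of timing. By plan, all patients are still on drug at month 2 and none has been classified as continuing or not. A month-2 analysis limited to continuers therefore drops scheduled scores because of something that happens later. Renewal requires a fall in joint count with a physician-judged response, a CDAI response, or skin improvement. It is plausible, though not shown in the documents, that early PRO change moves with these. If so, the patients kept are those who were already doing better. Month 2 is the one post-baseline visit that precedes every renewal decision, and the restriction would give up that advantage.

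**Working it through.** **1. The plan's own figure, used only as a yardstick.** Section 9.6 states "Approximately 80 subjects will be enrolled into each of these 2 parallel study groups", to detect "within participant effect sizes of approximately 0.40 as statistically significant" with 90% power at two-sided 0.05. The normal approximation gives n = ((1.960 + 1.282)/0.40)² = 65.7, so 66; the paired t-test needs 68. With 80, power at 0.40 is 94.2%, and the effect detectable with 90% power is 0.367. The stated size is somewhat conservative: 68/0.85 = 80, so an unstated 15% loss allowance would reproduce it. It is not in dispute.

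**2. Timing.**
- Month 2: no renewal decision has been made and, by plan, all patients are on drug. Any restriction to eventual continuers uses later information.
- Month 4: the decision may fall before or after the visit. Patients who stopped before month 4 have no score under either text. The two texts differ only for patients who have a month-4 score and stop later. The documents do not say how many that is.

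**3. Size of the shift at month 2.** Inputs not in the documents are assumed: the proportion continuing, p, and the correlation, ρ, between month-2 change (scaled to SD 1 and signed so that positive is improvement) and a latent normal response that decides renewal. With c = z(1 − p), the mean shift in continuers is ρ·φ(c)/p. For p = 0.7: c = −0.524, φ(c) = 0.348, φ(c)/p = 0.497. The shift is 0.3 × 0.497 = 0.149, or 0.5 × 0.497 = 0.248.

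| p | φ(c)/p | ρ = 0.1 | ρ = 0.3 | ρ = 0.5 |
|---|---|---|---|---|
| 0.9 | 0.195 | 0.02 | 0.058 | 0.097 |
| 0.8 | 0.350 | 0.035 | 0.105 | 0.175 |
| 0.7 | 0.497 | 0.050 | 0.149 | 0.248 |
| 0.6 | 0.644 | 0.064 | 0.193 | 0.322 |

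A true early change of 0.40 SD in all starters would thus appear as 0.55-0.65 at p = 0.7 and ρ = 0.3-0.5. At ρ = 0 there is no shift.

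**4. What this does to the test, if it is read as a statement about all starters.** Suppose the true mean change in all starters is zero. In continuers the SD is √(1 − ρ²λ(λ − c)), with λ = φ(c)/p. For p = 0.7 and ρ = 0.5 it is 0.934. With 80 × 0.7 = 56 continuers, the noncentrality is (0.248/0.934)·√56 = 1.99, and the nominal 5% paired t-test rejects 50% of the time.

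The number analysed differs by instrument. HAQ-DI and SIBDQ have about 80 starters each. For DLQI, Section 9.6 says "A minimum of 30 subjects with psoriasis will also be enrolled". The generic scales are pooled in Section 9.8.5, up to about 190. At p = 0.7, with every starter scored:

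| Starters | Continuers | ρ = 0.1 | ρ = 0.3 | ρ = 0.5 |
|---|---|---|---|---|
| 30 | 21 | 6% | 10% | 21% |
| 80 | 56 | 7% | 20% | 50% |
| 190 | 133 | 9% | 42% | 86% |

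Across p = 0.6-0.9 and ρ = 0.3-0.5, the range for 80 starters is 8-66%. Simulation (20,000 runs per setting) agrees: at p = 0.7, ρ = 0.5 and 80 starters, the shift is 0.25 SD and rejection about 50%. Testing all starters rejects about 5% of the time.

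**5. What stays valid.** In the same simulations, the 95% interval computed in continuers covers the continuers' own mean change about 95% of the time. The error lies in carrying that result over to all starters.

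**The case against.** The strongest reply is that Section 9.8 is the detailed analysis text and already states the sound rule, so no bias occurs unless the Abstract overrides it. That stands. A reader might infer that the plan commits itself to a biased early analysis; the documents do not support this. They support an unreconciled conflict, one side of which would introduce selection.

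Second, the term for the responder population is never defined. Read visit by visit, it could mean patients on drug at that visit, in line with Section 9.8.1.2, where observation ends when medication stops. No early score would then be discarded. This reading cannot be excluded, but the responder and non-responder labels and the months 3-6 criteria point to eventual continuers. The same edit settles either reading.

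Third, it is tempting to call the intervals and p-values wrong, or to say the means move upward. Step 5 shows that the intervals are sound for the group the Abstract names. On HAQ-DI, DLQI, K10 and WPAI:GH improvement lowers the score, so only a shift toward improvement can be claimed.

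Fourth, the size rests on assumptions. Correlation with renewal is easier to believe for the disease-specific indices than for the Flourishing Scale or K10, and a weak correlation leaves little shift. This also stands.

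Finally, the reach is limited. Sections 8.0 and 9.1 list these PROs as endpoints at month 6 only, early WHODAS is not in the restricted bullet, and month 4 is only partly affected.

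**Conclusion.** The point holds as a contradiction that should be reconciled. The Abstract and Section 9.8 give different populations for the month-2 and month-4 changes in seven secondary instruments. If the Abstract governs and means eventual continuers, the month-2 results, and the month-4 results for patients still on drug and undecided, are conditioned on a later outcome.

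As estimates for all starters, month-2 results would then be shifted toward improvement by about 0.06-0.32 SD of change. This assumes 60-90% continuation, a correlation of 0.3-0.5 and a normal selection model; at a correlation of 0.1 the shift is 0.02-0.06 SD. No single rejection rate describes all seven instruments, because the number analysed runs from about 30 to about 190. The month-4 shift cannot be sized from the documents.

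The point does not extend to the primary endpoint, to the month-6 population or to data after adalimumab stops. Adopting the full analysis set removes the early selection but leaves any month-6 question open.

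**What to change.** Reword the Abstract bullet so that months 2 and 4 are analysed in all patients who started adalimumab and have a score at that visit, whatever the later continuation decision, as in Sections 9.8.1.1 and 9.8.5. Define the responder population once, stating when a patient enters it, and do not use it to select early visits. If early change in later continuers is of interest, present it as a descriptive subgroup, with a note that it does not estimate the effect in all starters.

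The same edit can reconcile the test for the pooled scales, where the Abstract has paired t-tests and Section 9.8.5 has general linear models.

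The cost is wording only: no new data and no change to visits or treatment. The reported month-2 and month-4 changes may be somewhat less favourable than under a continuer-only analysis.

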5.0 Amendments and Updates

Number	Date	Section of Study Protocol	Amendment or Update	Reason
1	16SEP2015	
 Title Page Milestones Study Design Setting Management and Reporting of Adverse Events 	
 Addition of acronym to study title Update milestones based on FSFD Addition of guidance on discontinuation of individual subjects Addition of requirement around TB screening to inclusion criteria Clarification to Schedule of Events Addition of requirement around reporting of non-serious adverse events of malignancy in patients ≤ 30 years of age 	
 Increase physician recall of study Updated timelines Process has been unclear Observational study – Requirement for TB screening should follow local requirements and according to the approved adalimumab New Zealand Datasheet Clarification of what is required at Baseline and timing of questionnaires Global Regulatory requirement

A detailed summary of the changes is included in Annex 2.

